Appendix G.	Insulin Stability Experiment Report & Raw Data	32

List of Tables

Table 1: REDACTED	Error! Bookmark not defined.
Table 2: Study Design.....	9
Table 3: Study Visit Schedule	15
Table 4: Prohibited Medications.....	17

List of Figures

REDACTED

Definitions

Adverse event (AE)	Any undesirable patient experience that may include but is not limited to an abnormal sign, symptom, illness, abnormal laboratory value, or other medical event.
Cerebrospinal Fluid (CSF)	Clear liquid that flows around the brain and spinal cord.
Columbia-Suicide Severity Rating Scale (C-SSRS)	A scale designed to quantify the severity of suicidal ideation and behavior.
Data Safety Officer (DSO)	An independent individual with relevant experience assigned to review safety data to monitor for incidence of trends that would warrant termination of the trial.
Intranasal (IN)	A method of drug delivery that is particularly applicable to delivering centrally acting medications into the central nervous system.
Intranasal Insulin (INI)	Human insulin that is administered to the nose in effort to directly target delivery to the central nervous system
Lumbar Puncture (LP)	A medical procedure which involves inserting a needle between two vertebrae of the lower back to collect fluid surrounding the spinal cord and brain.
Serious adverse events (SAE)	Any symptom, sign, illness or experience that develops during the study and results in a life-threatening situation, hospitalization, significant disability, and other events determined by the investigator to be significant.

Protocol Summary

PROTOCOL TITLE	Measurement of Insulin Levels in CSF of Healthy Adults after a Single Intranasal Dose
SHORT TITLE	INI-CSF
STUDY PHASE	Phase I
STUDY OBJECTIVES AND PURPOSE	

Primary Objectives:
 
• To measure the concentration of insulin that reaches central nervous system in humans after intranasal administration	

Secondary Objectives:
 
• To describe the effect of single intranasal insulin dose on serum insulin in healthy adults	
STUDY DESIGN	
Study Type	Pharmacokinetics
Control Type	None
Study Indication Type	Pharmacokinetics
Blinding Schema	Unblinded
Study Drug	Regular, Human Insulin [rDNA origin] USP solution for injection 100 units/mL
Device	SipNose
Route	Intranasal
Study Design	Open-label, randomized
Planned Duration of Subject Participation	4-5 weeks (Treatment duration: 1 dose)
PRIMARY ENDPOINTS	

• Cerebrospinal Fluid (CSF) Insulin Levels at pre-defined times (0-40 Min)	
SECONDARY ENDPOINTS	

• Serum Insulin levels at pre-defined times (0-40 Min)	

INVESTIGATIONAL PRODUCTS, DOSE AND MODE OF ADMINISTRATION

Investigational Product	Regular insulin (Novolin-R) in 2 different doses (80, and 40 IU) (see Table 2)						
	

INI Dose	CSF Collection Times	

40 IU (n=6) 2 x 200 uL	0, 10, 20, 30, 40 min	

80 IU (n=6) 2 x 200 uL Wait 2 min 2 x 200 uL	0, 10, 20, 30, 40 min	

	INI Dose	CSF Collection Times	40 IU (n=6) 2 x 200 uL	0, 10, 20, 30, 40 min	80 IU (n=6) 2 x 200 uL Wait 2 min 2 x 200 uL	0, 10, 20, 30, 40 min
INI Dose	CSF Collection Times						
40 IU (n=6) 2 x 200 uL	0, 10, 20, 30, 40 min						
80 IU (n=6) 2 x 200 uL Wait 2 min 2 x 200 uL	0, 10, 20, 30, 40 min						

SUBJECT SELECTION

Targeted Accrual	Up to 12 subjects. We estimate a need to consent 25 participants to reach this goal.
------------------	--

INCLUSION CRITERIA

1. Subject is between ≥ 18 and ≤ 35 years of age
2. Subject's body mass index is between ≥ 18.5 and ≤ 24.9 , or can safely undergo a lumbar puncture at the discretion of the radiologist
3. Subject must be proficient in speaking English to comply with instructions and measures for the study
4. Subject can provide written informed consent
5. Female subjects must have either: (1) a negative pregnancy test at the screening and treatment visits OR (2) be at least 2 years post-menopausal / surgically sterile.

EXCLUSION CRITERIA

1. Subject has medical history and/or clinically determined disorders: chronic sinusitis, previous nasal and/or oto-pharyngeal surgery and severe deviated septum and/or other anomalies.
2. Subject has history of any of the following: active and significant central nervous system, psychiatric illness, pulmonary, or cardiovascular disorders or any other clinically relevant abnormality that inclusion would pose a safety risk to the subject as determined by investigator
3. Subject has participated in a clinical trial investigation within 3 months of this study.
4. Subject has an insulin allergy
5. Subject has Insulin-dependent diabetes
6. Subject is pregnant or breast feeding
7. Contraindication to spinal tap or other safety factors that preclude lumbar puncture in the investigator's opinion

1 Introduction

1.1 Background and Rationale

1.1.1 Intranasal Insulin

Intranasal (IN) delivery offers a non-invasive route to deliver large molecules such as insulin directly to the brain while minimizing systemic exposure. Peptides, proteins, vaccines, drug treatments and ions of various sizes are able to pass along the olfactory and trigeminal nerves and are deposited directly into the CNS without having to pass through the blood-brain barrier (BBB), which may degrade or limit the amount arriving at the target ¹⁻⁸. CSF insulin levels in healthy adults have been detected as early as 10 minutes following IN delivery (Appendix A) while not measurably increasing systemic blood-glucose levels ^{3,9}. Similar observations of the safety of intranasal insulin (INI) have been made in memory impaired adults ^{10,11}.

Originally thought to exist solely in the periphery, insulin has since been determined to be instrumental in the overall health and function of the CNS ¹². Central insulin and insulin receptors (IRs) have been established as differing from that of the systemically occurring counter parts that specifically regulate glucose utilization. In rodents, insulin receptors and insulin-sensitive glucose transporters are selectively co-localized in brain areas responsible for memory, thus providing a platform for insulin signaling whereby selective increases in cerebral glucose utilization could modulate memory ^{13,14}. Consistent with evidence of insulin functioning as a neuromodulator for memory-related function is the high-density of IRs in the hippocampus and cerebral cortex, brain regions integral to the formation, retention and recall of information ^{12,15}. Systems with impaired insulin signaling pathways have demonstrated inhibition of acetylcholine biosynthesis and subsequently have incurred debilitating effects on neuronal plasticity ^{16,17}. Increased insulin resistance and glucose intolerance has been observed in a multitude of neurodegenerative processes including Alzheimer's disease ¹⁴, Parkinson's disease ¹⁸, and Huntington's disease ¹⁹.

Clinical studies with INI in the last 20 years have studied it as a therapeutic option for multiple diseases including Alzheimer's dementia (AD), Parkinson's disease, and Post-traumatic stress disorders. In addition, studies in healthy humans and patients have shown effects on metabolism, including reductions in food intake, body weight, improvements of glucose uptake, and possible influence on mood, addiction, and sleep ²⁰. Recent studies have shown that INI also reduces white matter damage in the brains of patients with Alzheimer's Disease²¹. Appendix A provides an overview of the multiple studies conducted with INI. In Appendix B, Tables 1 (acute INI, 38 studies) and 2 (chronic INI, 18 studies) from the Schmid review provide key effects of INI on functional outcomes such as cognition, or memory.

The delivery of drugs to the CNS remains a development challenge mainly due to the blood-brain barrier limiting access. Commercially available aerosol nasal devices such as the LMA MAD device are not specifically engineered to facilitate nose-brain delivery, and consequently deposit most of the drug within the lower nasal cavity, resulting in suboptimal CNS penetration. Furthermore, there is concern about variable, user-dependent drug delivery due to dependency upon subject positioning and inconsistent volume ejection.

1.1.2 Intranasal Insulin and Devices

REDACTED

1.1.3 Safety of Intranasal Insulin

Novolin R has been approved for subcutaneous or intravenous use since 1991. The most common side effect noted with these two routes is hypoglycemia (Regular Insulin, Drug Monograph; Appendix D). A recent review of safety of IN human insulin trials revealed no safety concerns, with no serious adverse events or symptomatic hypoglycemia in a total of 1092 individuals studied²⁸. In Appendix B, Tables 1 (acute) and 2 (chronic) of this review provide a summary of the human studies with INI. The majority of the studies used regular Insulin (Novolin R or Actrapid, Humulin R, Insuman Rapid, H-insulin 100) with similar excipients and none are believed to be in a range that causes harm²⁹.

Study of pharmacokinetics of INI in mice showed only 3% of INI entered the circulation and no peripheral metabolic effects were detected up to a day after IN administration³⁰. Treatment with 40 IU INI in humans found no significant changes in circulating insulin levels, suggesting that INI does not pass into the circulation^{3,9}. A recent study in cardiac surgery patients, intranasal administration of insulin at doses of 40 IU and 80 IU did not cause hypoglycemia intraoperatively³¹. Though some studies with higher doses (160IU) have shown small detectable increase in insulin levels, no significant change in blood glucose levels were noted³². Notably, intranasally administered insulin improves memory in healthy adults and Alzheimer's patients without altering blood levels of insulin or glucose^{11,33-39}.

The most common side effect with INI administration noted is transient local or nasal irritation. In Appendix B, please refer to Table 3 of the Schmid et al., 2018 review for a summary of the local or nasal effects of INI in humans. In 2012, Craft et al reported, that number of adverse events was higher for the 20 IU and 40 IU when compared to the placebo group; however, there were no SAE's and mostly minor AEs such as rhinitis were reported (Table 4, ³⁵). Similar minor AEs were reported in the 2017 by Craft et al using INI (Supplementary table 2, ³⁹). Similar findings were reported in recent meta-analyses⁴⁰ and the most recent trial on INI²⁶, which showed no clinically relevant adverse events during the chronic administration of 40 IU of insulin with two different administration devices. Overall, INI at the proposed dose in this protocol, is expected to be safe with limited side effect profile. We do plan to monitor the subjects for hypoglycemia.

2 Summary of Device Description

2.1 Intranasal SipNose Device Overview

REDACTED

2.1.1 Intranasal SipNose Device

REDACTED

2.1.1.1 Reliability

REDACTED

2.1.1.2 Safety

REDACTED

2.1.1.3 Device-Drug Contact and Safety

REDACTED

3 Study Objectives

3.1 Primary Objective

- To measure the concentration of insulin that reaches cerebrospinal fluid in humans after intranasal administration

3.2 Secondary Objective

- To describe the effect of single intranasal insulin dose on serum insulin in healthy adults

4 Study Endpoints

4.1 Primary Endpoints

- Cerebrospinal Fluid Insulin Levels at pre-defined times (0-40Min)

4.2 Secondary Endpoints

- Serum Insulin levels at pre-defined times (0-40 Min)

4.3 Safety

- Incidence and severity of serious adverse events (SAEs) and adverse events (AEs)
- Frequency of change in clinically-significant vital signs
- fingerstick glucose level <70mg/dl

5 Study Design

This Phase 1 is a single center, open-label, randomized pharmacokinetic study designed to describe the central nervous system delivery of intranasal insulin to CSF using anIN delivery device.

Table 1: Study Design

INI Insulin Dose	Collection Times
40 IU (n=6) 2 x 200 μ L (0.2ml)	0, 10, 20, 30, 40 min
80 IU (n=6) 2 x 200 μ L (0.2ml) Wait 2 min 2 x 200 μ L (0.2ml)	0, 10, 20, 30, 40 min

After written informed consent has been obtained, subjects will be screened to assess study eligibility based on study inclusion/exclusion criteria. Subjects who are eligible at the end of the screening visit will be randomized and assessed for outcome measures, including lumbar puncture and CSF/blood draw following a single dose of INI administered by the trained research staff. Randomization will be stratified by gender to ensure a balanced distribution of male and female participants within each group. A Block randomization scheme will be employed to ensure that the final group sizes are equivalent.

5.1 Justification for Study Design, Dose and Endpoints

5.1.1 Justification for Study Design and Dose

In this study, we will be measuring the concentrations of insulin in the CSF of 12 healthy adults after IN administration of one of two doses of insulin: 40 IU and 80 IU (Table 2). Multiple clinical trials of INI have ranged from 10 IU -160 IU for a variety of disorders, have been found to be safe in healthy adults⁴⁵ and are the basis for dose selection in this study. The higher dose (80 IU) may be the maximum feasible dose for

clinical studies, while the lower dose is the most encountered dose in clinical studies (both acute/chronic). The INI doses proposed are both safe, and are known to improve function or outcomes in the respective disorders. In addition, our research group has completed ([NCT01436045](#), [NCT02432716](#), [NCT02503501](#), [NCT04028960](#)) or has ongoing ([NCT04115384](#), [NCT04251585](#)) INI based clinical trials with similar doses and designs that are summarized in Appendix F.

Figure 7. REDACTED

5.1.2 Justification for Endpoints

The key objective of this study is to provide essential information on the ability of device to target INI to the brain and spinal cord as measured in CSF collected by lumbar puncture, which is the primary endpoint for the study. Born et al (2002)³ (Appendix E) demonstrated detection of insulin after intranasal administration of 40 IU using a metered dose spray pump. Our study will measure the concentrations of insulin that reach the CSF following administration using an intranasal delivery system. The secondary endpoint will provide additional information regarding the concentration of insulin in serum.

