7.3.2 Neurological Examination

Neurological examination will be performed at visits 1, 3 or if the subject withdraws early. Any abnormalities noted at Visit 1, will be documented as part of the subject's medical history.

7.3.3 Vital Signs:

Vital signs will be recorded at all three study visits. Diastolic blood pressure will be measured at the disappearance of Korotkoff sounds. Vitals sign will be monitored by clinical staff during screening and lumbar puncture visits of the study.

Serum Glucose will be examined at visit 1 (screening) and visit 3 (safety follow-up). Fingerstick glucose tests will be performed at visit 2 (LP procedure). A blood glucose < 70 mg/dL will be considered clinically significant. The likelihood of peripheral hypoglycemia is low based on numerous clinical trials performed showing no effects of INI on peripheral glucose.

7.3.4 Weight:

Body weight will be measured at all three study visits.

7.3.5 Laboratory Samples:

All the laboratory samples will be drawn independent of fasting or non-fasting status.

When a patient withdraws from the study, samples collected prior to the date of withdrawal may still be analyzed, unless the patient specifically requests that the samples be destroyed or local laws require destruction of the samples. However, if samples have been tested prior to withdrawal, results from those tests will remain as part of the overall research data. Samples will be collected and processed according to the standard procedures. Key planned labs include:

- Basic Metabolic Panel
- Complete Blood Count
- Blood Coagulation Tests

7.3.6 Point-of-Care Glucose Testing:

At Visit 2, the participant will receive a single dose of intranasal insulin administered prior to their lumbar puncture. Point-of-care fingerstick glucose testing will be performed once before the administration of the study drug (baseline glucose reading) and twice after the administration of the drug according to the following schedule:

- (1) 15 minutes after study drug dosing (between the 2nd and 3rd CSF/serum samples are collected)
- (2) 45 minutes study drug dosing (after the final CSF/serum samples are collected)

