7.3.11 Pharmacokinetic Sampling

The study team will attempt to collect the CSF and serum samples as close in time as possible for each PK time point. Given differences in how serum/CSF are extracted for this study, there may be a slight difference between collection start and stop times. To ensure consistency across participants, the study team will initiate collection of the CSF samples first, followed by the serum samples, at each of the 5 PK time points.

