12.2 Statistical Analysis of Primary and Secondary Endpoints

Primary Endpoints: We will utilize immunoassay to analyze the CSF samples to determine the levels of Insulin concentration at the specified times. We will graph these values across time for each subject using line graphs. We will also graph the sample average Insulin concentration across time, and at different doses with error bars and report concentrations as mean \pm SE. Finally, the concentrations will be analyzed using common pharmacokinetic measures including the peak concentration (Cmax), time to peak concentration (Tmax), and area under the curve (AUC). This type of analysis is very similar to that done in Dhuria's 2009 publication in the *Journal of Pharmaceutical Sciences*, on which [name] and [name] were co-authors. Similar analysis will be conducted for secondary endpoints.

AEs and SAEs will be categorized and summarized by study group. We will descriptively note if any group was more likely to have experienced a particular AE/SAE or generally experienced more AEs/SAEs throughout the course of the study.

13 Study Conduct Considerations

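### Section 12.2 plans no change from baseline and no paired CSF–serum analysis, so its summaries would not on their own support a targeting reading if serum insulin also moves

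*Combined protocol and SAP*

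**What the plan says.** The formal primary objective (Section 3.1) is descriptive: "To measure the concentration of insulin that reaches cerebrospinal fluid in humans after intranasal administration". The secondary objective (Section 3.2) is to describe the effect of the dose on serum insulin. Section 5.1.2 goes a step further. It says the study is to inform on the "ability of device to target INI to the brain and spinal cord as measured in CSF", and gives serum a supporting role: "The secondary endpoint will provide additional information regarding the concentration of insulin in serum".

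The sampling is built for pairing. Under Section 7.3.11, "The study team will attempt to collect the CSF and serum samples as close in time as possible for each PK time point", and staff are to "initiate collection of the CSF samples first, followed by the serum samples, at each of the 5 PK time points". Sections 7.3.11.1 and 7.3.11.2 give the same five times and the same immunoassay for both fluids, with a detection limit of 0.1 µIU/mL.

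Section 12.2 plans for CSF a line graph per subject, mean curves by dose with error bars, mean ± SE, Cmax, Tmax and AUC. Serum is covered by one sentence: "Similar analysis will be conducted for secondary endpoints". No subtraction of the 0-minute value is specified, and nothing relates the two fluids. The Protocol Summary lists no control and names regular human insulin as the study drug.

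**The concern.** Targeting is a statement about CSF relative to blood. A CSF rise with flat serum points towards direct delivery. A CSF rise alongside a serum rise has at least two explanations: direct delivery, or passage of insulin from blood. A higher CSF level at 80 IU than at 40 IU does not choose between them, because both routes could deliver more at the larger dose.

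The drug is human insulin, and the assay is not described as telling administered from endogenous insulin. Raw Cmax and AUC therefore include whatever insulin was present before dosing. At stake is whether the trial can say, from data it already collects by lumbar puncture, how much CSF insulin changed after dosing and whether that happened with or without a change in serum.

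**Working it through.** The plan gives no power, precision or insulin figure, so there is no stated result to reproduce. The check has five steps.

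**1. What is collected.** Six participants per arm and two arms give 12. Five times each gives 12 x 5 = 60 pairs, of which 12 x 4 = 48 are after dosing. These are repeated measures in 12 people, not 60 independent observations.

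**2. What raw summaries contain.** With samples every 10 minutes, the trapezoidal rule gives AUC0-40 = 10 x (C0/2 + C10 + C20 + C30 + C40/2). If nothing is delivered and CSF stays at C0, then Cmax = C0 and AUC0-40 = 10 x 4 x C0 = 40 x C0. Both are above zero with no delivery at all. The baseline-corrected form, AUC0-40 − 40 x C0, is then zero. The 0-minute sample makes this correction possible; Section 12.2 does not specify it.

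**3. Whether serum may move.** Section 1.1.3 reports no significant change in circulating insulin at 40 IU in humans and a small detectable rise in some studies at 160 IU. For 80 IU it cites the absence of hypoglycaemia during cardiac surgery, which is a glucose finding. It also says that memory studies found blood insulin unaltered, without giving their doses. No human serum insulin result is tied to 80 IU, so the question is open at the upper study dose.

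**4. What the planned outputs can show.**
- CSF rises, serum flat: the per-subject curves in both fluids show this, and blood is an unlikely source.
- CSF flat: there is no rise to attribute.
- CSF rises, serum rises: separate curves, Cmax and AUC do not show whether participants with larger serum rises are those with larger CSF rises. Nothing specified addresses this.

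A simulation of 20,000 trials per setting illustrates the last case. Assumptions: log-SD 0.6 for the serum rise; residual log-SD 0.2, 0.4 or 0.6 for the CSF rise; and the same CSF and serum distributions whether CSF insulin came from blood or independently of it. Separate group summaries then agree under both mechanisms. A paired correlation (two-sided 0.05) flagged pure spill-over in 94, 63 and 38% of trials at n = 6, and in 100, 97 and 79% at n = 12. It gave about 5% false flags when the two rises were independent. That last figure depends on independence: if the amount of drug retained in the nose varied, it could drive both rises and produce a correlation under direct delivery too.

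**5. Precision of a paired analysis.** For a geometric mean CSF:serum ratio, the 95% CI is the estimate multiplied and divided by exp(t x √ln(1 + CV²) / √n), with t = 2.571 at n = 6 and 2.201 at n = 12. The CV is assumed, because the documents give none:
- n = 6: 1.36, 1.64, 2.09 and 2.40 for CVs of 30, 50, 80 and 100%.
- n = 12 (arms pooled): 1.21, 1.35, 1.56 and 1.70.

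For a correlation, the critical value is t / √(n − 2 + t²) on n − 2 degrees of freedom:
- n = 6: 2.776 / √(4 + 7.71) = 0.81.
- n = 12: 2.228 / √(10 + 4.96) = 0.58.

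The true correlation needed for 80% power is tanh((1.960 + 0.842) / √(n − 3)), which is 0.92 at n = 6 and 0.73 at n = 12. This is exploratory precision.

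**The case against.** The strongest reply is that the formal objectives are to measure and to describe, and the plan does both. Section 5.1.2 speaks of providing information on targeting, not of proving it, and sets no hypothesis or decision rule. This stands, and it confines the point to the interpretation in Section 5.1.2.

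A reader might infer that the plan cannot separate delivery from spill-over. The documents do not support that. Section 12.2 plans a curve for each subject and a similar analysis for serum at the same times, so flat serum with rising CSF, as Section 1.1.3 leads one to expect at 40 IU, would be visible.

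A reader might also infer that insulin sampling disregards fasting. The sentence "All the laboratory samples will be drawn independent of fasting or non-fasting status" stands in Section 7.3.5, whose listed tests are metabolic panel, blood count and coagulation. Section 7.3.11 is silent on fasting, and the content of the pre-procedure instructions is not shown. One can say only that the visible text states no fasting requirement for Visit 2.

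Nor does Section 5.1.2 claim that this device is superior to another, so no disclaimer is needed there.

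Two limits on the remedy also stand. A ratio relative to 0 minutes, (Ct/C0) / (St/S0), rises when serum merely falls: with CSF unchanged and serum at an assumed 80% of baseline, it is 1/0.8 = 1.25. And with unlabelled human insulin, no control and sampling that ends at 40 minutes, pairing cannot establish origin, and a delayed passage from serum to CSF may be missed.

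Finally, Section 12.2 refers to a 2009 publication for the style of analysis, and the device sections are redacted. The point concerns the visible text.

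**Conclusion.** The gap is real and modest. Section 12.2 specifies neither a change from the 0-minute value nor any paired analysis, and its summaries alone would not support a targeting reading if serum insulin also moves. If serum stays flat, the planned curves suffice informally. The condition is left open at 80 IU by the documents' own evidence.

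No bias can be sized, since no CSF or serum insulin values are given. The 3% mouse figure in Section 1.1.3 is not used for this: it would need an assumed distribution volume and no elimination, and it would sit poorly with the human result at 40 IU. The simulation and CI widths rest on assumed variances. They show that the pairs carry information the plan leaves unused, and that this information is imprecise at n = 6. The change should be made before the data are analysed; the formal objectives do not depend on it.

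**What to change.** Add to Section 12.2, labelled exploratory:

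- (a) For each participant, the change from the 0-minute value in CSF and in serum at each time, with baseline-corrected Cmax and AUC0-40 by dose and 95% CIs. Because the corrected Cmax is the largest of four post-dose differences, it tends above zero even without delivery; its interval should not be read as a test against zero.
- (b) A plot of CSF change against serum change, with each participant identifiable.
- (c) The CSF:serum ratio relative to 0 minutes, reported only alongside the absolute changes because it also rises when serum falls. State a rule for values below 0.1 µIU/mL: for example, report the number of such values at each time and leave the ratio uncalculated where either value is below the limit.

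State in Section 5.1.2 that, without a control and with unlabelled human insulin, a CSF rise accompanied by a serum rise will not be read as evidence of direct delivery, and that the paired analysis supports but does not prove origin.

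Because (a) to (c) depend on the 0-minute value and on the order within each pair, two sets of passages must be reconciled. Section 7.1.2 places CSF collection second under the serum bullet, against first in its CSF bullet and in Section 7.3.11. Section 7.3.6 places the dose before the lumbar puncture, while Section 7.1.2.1 takes a CSF sample before the dose.

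Cost: a small amount of extra analysis and a short addition to Section 5.1.2. No new samples or procedures are needed. The downside is imprecise estimates at six per arm, which the exploratory label should make plain.
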